#### **Study design**

The study is a double-blind pilot trial on outpatient patients, followed in an integrated way at a specialized center for the care of diabetic foot and Home Care as territorial home nursing service, articulated over a total period of 24 weeks (20 weeks of treatment plus 4 weeks of observation). Therefore, after an initial characterization and treatment setting by the specialist center, the patients will be followed biweekly by the nurses of Home Care, to then be re-evaluated at the center on a monthly basis.

The assessment of the evolution of the lesions will be made at the specialist center, in which the evaluating physician will not be aware of the type of home treatment performed by the patient and its allocation group and the execution of treatment with EmoLED will be performed ensuring the blindness also to the patient. This also ensures an adequate level of masking to ensure that the study is double-blind.

Both for the treatment group and for the control group, the patient will not be aware of the group to which he has been assigned; the operator will make the patient wear glasses (distributed to each patient at the beginning of the study) totally obscuring and will take out of the room any family members or other people before performing/simulating the treatment with the EmoLED device. In case the patient has been assigned to the control group, the operator will simulate to perform the treatment, turning on the device but pointing the light beam away from the patient (e.g. illuminating the floor).

Once the inclusion criteria are verified and the patient has given their consent to participate in the study, a two-week pre-enrollment period will be observed, in which the patient will receive standard treatment (as

indicated below); at the end of the two weeks of pre-enrollment, the patient will be re-evaluated to see if the lesion has not reduced by 50% with standard treatment alone.

If so, the patient will leave the study while, if the lesion has not reached this percentage of re-epithelialization, the patient will be randomized into the two study groups: the control group will continue with only the standard treatment as described above, while the treatment will receive in EmoLED treatment in addition to the standard treatment.

Patients will be randomized into the two arms of the study according to a list of random numbers generated by special IT tools and communicated by the scientific supervisor to the Care Provider via e-mail.

It is a 1: 1, single-block randomization of 40 patients distributed in the two groups (treated and control). After the two-week enrollment observation period, the Investigator at the outpatient center will ascertains the conditions for the study prosecution and he will notify the Head of the Care Providers to take charge of the patient included in the study and to proceed with the assignment to one of the groups. In this way, the Investigator at the outpatient center will be blinded to the treatment performed at home by the patient.

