#### *Inclusion Criteria:*

- *Patients suffering from neuro-ischemic diabetic foot ulcer grade IC or IIC according to the University of Texas Wound Classification (22); If the patient has two or more lesions, which may fall within the inclusion criteria, the most serious lesion (index lesion) will be selected and followed for the entire duration of the study;*
- *Patients who, following hospital discharge or after the first outpatient assessments, are followed by Home Care Nursing Service and are always monitored at the same referral center;*
- *Patients with type I or II diabetes, with glycated haemoglobin≤ 10%;*
- *Patients willing to constantly wear the offload devices prescribed by the reference center;*
- *Patients with ulcer localized on toes, on the plantar side, on the margins or on the dorsum of the foot wider than 1 sqcm;*
- *Patients with peripheral neuropathy confirmed with Monofilament (Semmes-Weinstein 5.07 / 10g);*
- *Patients with ABPI of 0.7 - 0.9, ankle PA> 70mmHg, TcPO2 between 36 - 50 mmHg;*
- *Patients with lesions lasting from 1-24 months;*
- *Patients who understand the purpose of the Clinical Study and provide their informed consent in writing.*

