### **Quality assurance, control procedures, data management and record-keeping**

All the information gathered during the Study will be considered strictly confidential. The patients' consent to the registration of personal data will be requested at the time of recruitment; nevertheless, the data collection forms will contain the Identification Code of the patient and their date of birth only.

In order to guarantee the correct traceability of all parties involved, the number of the Study and the naming of the Center will be included as well.

At the end of the Study, all data will be archived using the appropriate safety measures at the Coordinating Site for a minimum of ten years.

If a patient withdraws their consent to data processing, they will be immediately destroyed to ensure total confidentiality. In addition, each investigator will keep a copy of the study's documentation for at least two years after its conclusion.

The principal investigator creates and is responsible for updating and maintaining the Patient Identification Register, or Enrollment Register, and is responsible for the implementation of appropriate organizational measures to protect such information in order to prevent unauthorized access and dissemination or accidental destruction or loss (e.g. keeping under lock and key study material containing sensitive data).

The register shall contain the personal data of the patients giving their consent to participate in the study, the identification code assigned to the patient, the indication of any exit from the study, with the relative motivation and the date of recruitment.

The patient code consists of a two-digit number (numerical progressives), starting from 01. The patient code is reported in the data collection forms and in all documents that record data related to the trial, such as questionnaires, list of visits, photographic recordings and so on. Only the principal investigator and, at the discretion of the principal investigator, the members of their team are aware of the identity of the patients enrolled in the study.

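### The randomisation list is e-mailed to the unblinded home-care service that makes the assignments, with no rule for sequential release or order of use, so concealment at the assignment step is not assured

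*Protocol*

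**What the plan says.** All of the allocation procedure stands in the protocol's Study design section.

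- **List.** Patients are allocated from "a list of random numbers generated by special IT tools and communicated by the scientific supervisor to the Care Provider via e-mail". The ratio is 1:1 in one block of 40, which gives 20 per arm.
- **Decision to proceed.** After the two-week run-in on standard treatment, "the Investigator at the outpatient center will ascertains the conditions for the study prosecution".
- **Assignment.** Then "he will notify the Head of the Care Providers to take charge of the patient included in the study and to proceed with the assignment".
- **Stated purpose.** The arrangement is meant to ensure that "the Investigator at the outpatient center will be blinded to the treatment performed at home by the patient".

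The same section has the home-care operator perform or simulate the treatment. The home-care data collection form (Annex C) records the patient's code and group. Home Care is therefore unblinded by design.

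The section Quality assurance, control procedures, data management and record-keeping describes the enrolment register: personal data of consenting patients, identification code, any exit with its reason, and date of recruitment. On codes it says: "The patient code consists of a two-digit number (numerical progressives), starting from 01". Neither list position nor date of assignment is among the listed contents. The section Bias - systematic errors covers staff training and sponsor availability and does not mention allocation.

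**The concern.** Concealment has two parts. The person who decides that a patient enters must not know the next arm, and a patient who has entered must receive the next unused assignment and no other. The protocol deals with the first by keeping the list from the Investigator. For the second it gives the list to the service that assigns and treats, and states no rule that binds a patient to a list position.

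If the list is held whole, the head of the service learns who the patient is at notification, before assigning, and can see every unused slot. A patient expected to do well or badly could be given a slot out of order, by intent or by carelessness. Randomisation is this small trial's main protection against imbalance in ulcer severity, and masking of the patient and the evaluating physician does not repair a difference created at allocation.

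**Working it through.** **1. The plan's own figure.** The protocol declines a power calculation, so there is none to reproduce. One 1:1 block of 40 gives 20 + 20 = 40, which agrees with the Sample Size and Statistics sections.

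**2. Who knows and does what** (Study design, Patient selection, Annex C description):

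| Step | Party | Sent the list? |
|---|---|---|
| Identify consecutive eligible patients | Specialist centre | No |
| Judge the run-in result and decide who proceeds | Investigator | No |
| Assign to an arm | Head of the Care Providers | Care Provider receives it |
| Give real or simulated treatment, record the group | Home Care | Knows the arm |

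The gap is confined to the third row.

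**3. What the holder knows.** If the list is sent whole, 40 of 40 assignments are known in advance. If it is sent line by line and used in order of notification, none is known from the list itself, and only guessing from past assignments remains (step 5). The text says that a list is communicated, which most naturally means the whole list, but it does not say so expressly.

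**4. What a misplaced slot could do.** Suppose one better-prognosis patient due for control and one poorer-prognosis patient due for treatment exchange places. The share of better-prognosis patients rises by 1/20 = 5 percentage points in the treated arm and falls by 1/20 = 5 points in control, so the difference moves by 10 points. Two such exchanges move it by 20. This is an illustration: nothing in the protocol allows the number of exchanges to be estimated.

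**5. Is the single block a weakness?** Take staff who do not hold the list, see past assignments, and always guess the arm used less so far. For a block of n + n, the expected number of correct guesses is n + 2^(2n−1)/C(2n, n) − 1/2.

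- n = 20: 20 + 2^39/C(40, 20) − 0.5 = 20 + 3.99 − 0.5 = 23.49 of 40, or 58.7%. Simple randomisation gives 20 of 40, or 50%.
- The certain run at the end of the block averages 2n/(n + 1) = 40/21 = 1.90 patients. The probability that it is at least 3 is 2·C(37, 20)/C(40, 20) = 0.23.

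Under the same rule, for other schemes (the block sizes are assumptions; the random-size figures are simulated):

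| Scheme | Correct of 40 | Percent |
|---|---|---|
| Simple randomisation | 20.0 | 50 |
| One block of 40 | 23.5 | 59 |
| Random blocks of 6, 8 or 10 | 26.3 | 66 |
| Random blocks of 4, 6 or 8 | 27.0 | 68 |
| Random blocks of 2, 4 or 6 | 28.0 | 70 |
| Fixed blocks of 4 | 28.3 | 71 |

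The single block is less predictable than any smaller-block scheme shown. Withholding the block sizes does not help, because the rule uses only past assignments. The weakness is who holds the list.

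**6. Could the records show a departure from list order?** Codes cover everyone who consents, including patients who leave after the run-in. The Statistics section expects about 30% to improve by more than half in the first two weeks. As an illustration, 40 randomised patients would need about 40/0.70 = 57 entering the run-in, so codes and list positions would not match directly. However, removing the recorded exits and ordering the rest by recruitment date, with a run-in of fixed length, gives an approximate order of entry to compare with the group on the home-care forms and with the supervisor's list. A partial check is possible; an exact one is not, because list position and assignment date are not required.

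**The case against.** The strongest reply is that the design shields the person who matters most. The Investigator recruits consecutive patients, applies a measured 50% rule at the end of the run-in, decides who proceeds, and is not sent the list. That stands. A reader might infer from the e-mailed list that Home Care controls when patients enter; the Study design section does not support this.

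A reader might also infer that Home Care already treats patients during the run-in while holding their future assignments. The inclusion criteria concern patients who "are followed by Home Care Nursing Service and are always monitored at the same referral center", and standard dressings may be done at home, which makes earlier contact plausible. But the protocol does not say who delivers run-in care, and it has Home Care take over a patient after the Investigator's notification. The point does not need this inference, because the assigning party knows the patient at notification in any case.

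It can further be said that 40 patients in about 18 months is one every 78/40 ≈ 2 weeks, so two patients seldom become ready together. This limits swaps between simultaneous patients, but a holder of the whole list with no order rule can take any unused slot for a single patient.

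Finally, the trial is a proof of concept in which the patient and the evaluating physician are masked. That limits bias in outcome assessment; it does not address how patients are matched to arms.

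**Conclusion.** The point holds in a limited form. The protocol sends the list to the unblinded service whose head assigns, and it requires neither release of one slot at a time nor use of slots in order of notification. Concealment at the assignment step is therefore not assured. If the list is sent whole, which is the plain reading, all 40 assignments are visible to the assigning party; if it is sent line by line and used in order, the problem largely disappears, and the protocol need only say so.

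The documents do not support saying that allocation is certainly unconcealed, that no record could reveal a departure from list order, or that the single block of 40 is at fault. The change should be made before the first patient is randomised, because concealment cannot be restored afterwards.

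**What to change.** Amend the allocation paragraphs of the Study design section:

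1. The list is held by a named role outside Home Care and outside the assessing team. The scientific supervisor can do this if not an assessor.
2. After the run-in, the Investigator sends that person a dated confirmation of eligibility with the patient code.
3. That person then releases to Home Care only the next unused assignment, for that code, and logs code, list position, date and time. Slots are used strictly in the order in which confirmations arrive.
4. Keep the single 20:20 block. Simple 1:1 randomisation is an acceptable alternative, at the price of slightly unequal arms. Do not introduce small or randomly sized blocks.

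The cost is about 40 short e-mails and one log. Keeping the single block leaves sample size, treatment and analysis as they are. If sequential release is already intended, adding the sentence that says so, with the log, is enough.

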### **Patient selection**

All consecutive patients treated at the specialist outpatient center for diabetic foot care who meet the criteria listed below will be considered for inclusion in this study. Patients will be evaluated using a standard procedure that includes the collection of the medical history and a physical examination of the patient.

#### *Inclusion Criteria:*

- *Patients suffering from neuro-ischemic diabetic foot ulcer grade IC or IIC according to the University of Texas Wound Classification (22); If the patient has two or more lesions, which may fall within the inclusion criteria, the most serious lesion (index lesion) will be selected and followed for the entire duration of the study;*
- *Patients who, following hospital discharge or after the first outpatient assessments, are followed by Home Care Nursing Service and are always monitored at the same referral center;*
- *Patients with type I or II diabetes, with glycated haemoglobin≤ 10%;*
- *Patients willing to constantly wear the offload devices prescribed by the reference center;*
- *Patients with ulcer localized on toes, on the plantar side, on the margins or on the dorsum of the foot wider than 1 sqcm;*
- *Patients with peripheral neuropathy confirmed with Monofilament (Semmes-Weinstein 5.07 / 10g);*
- *Patients with ABPI of 0.7 - 0.9, ankle PA> 70mmHg, TcPO2 between 36 - 50 mmHg;*
- *Patients with lesions lasting from 1-24 months;*
- *Patients who understand the purpose of the Clinical Study and provide their informed consent in writing.*

#### *Exclusion Criteria:*

- *Patients who have participated in a clinical study with a drug or medical device for less than a month;*

- *Patients who are unable to understand the aims and objectives of the study;*
- *Patients who are bedridden or unable to walk or Patients with neoplasms;*
- *Patients with pressure ulcers;*
- *Patients who have infectious signs according to IDSA criteria;*
- *Patients who underwent revascularization in the previous two months;*
- *Patients who have presented an acute ischemic event within the previous 3 months;*
- *Patients with heel injuries;*
- *Patients with nephropathy undergoing dialysis;*
- *Patients with osteomyelitis;*
- *Patients with Charcot's neuro-arthropathy;*
- *Patient on high dose corticosteroid therapy ( $\geq 40$  mg/day);*
- *Patients with a history of self-harm who can voluntarily alter the course of healing;*
- *Patients with psychiatric disorders;*
- *Women who are pregnant or breastfeeding (the state of pregnancy or breastfeeding will be certified on the basis of the patient's declaration);*
- *Patients with pathologies or under treatment with drugs that induce photosensitization of the skin;*
- *Patients with a life expectancy of less than one year.*

In order to be eligible for the planned treatment phase, all the inclusion and exclusion criteria must be met. Any concomitant pharmacological therapy must be maintained.

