### **Medical-surgical procedures and study follow up**

Standard treatment, according to the most recent version of the IWGDF guidelines (IWGDF – International Working Group on Diabetic Foot < <https://iwgdfguidelines.org/wp-content/uploads/2019/05/IWGDF-Guidelines-2019.pdf> > ), includes debridement of the lesion, offloading with a device up to the calf, non-

removable (except for contraindications), dressing of the wound with advanced dressings in use at the trial center and at the home care according to SoC, to be renewed biweekly.

For the purposes of the study, in order to standardize the standard treatment as much as possible, all patients, except for contraindications, will adopt the same brace, made irremovable [Optima Diab, Molliter, Civitanova Marche (23-24)]

The treatment with EmoLED, in addition to the standard treatment, will be performed twice a week in correspondence with the dressing change of the lesion by the Home Care Nursing Service, blinded to the doctors of the specialist center, for twenty consecutive weeks, for a total of 40 treatments.

Treatment with the EmoLED device consists of irradiating each area of 5 cm in diameter of the lesion for 2 minutes; if the lesion is wider than 5 cm in diameter, the applications will be repeated to cover the entire area of interest. EmoLED treatment is additional to standard patient therapy.

During the twenty weeks of treatment with the EmoLED device and until healing, treatments with other types of phototherapies (including photodynamic therapies), topical negative pressure therapy, or other therapeutic interventions in addition to standard therapy will not be allowed.

In the event of clinical signs of infection of the wound, in the case of mild, moderate or severe infection according to I.D.S.A. (25), the lesion will be treated with antiseptic medication and, if deemed necessary by the investigator, with systemic anti-infective therapy, identified by medical personnel. The onset of infection will be reported in the appropriate section of the Data Collection Form and eventually reported to the promoter in case of serious infection (Serious Adverse Event).

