In case, therefore, the lesion presents signs of infection as described above, the patient will interrupt their presence in the study and will be treated adequately. The patient can continue the study only if there is a remission of the symptoms of infection. The event will be reported in the appropriate section of the Data Collection Form.

The patient will be invited to a scheduled check-up at the referral center to assess the progress of the lesion, once every 30 days, or as needed.

The patient, if the wound healing occurs while being managed at home, will be invited to return for a check-up visit at the referral center within a week, to confirm the healing.

If at the conclusion of the participation of the patient in the clinical investigation, any additional treatments are required to those normally provided for the clinical condition considered in this study, the sponsor will cover the costs incurred for such treatments.

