At each visit the investigator marks with an "X" the chosen value for each parameter and the most suitable description. The investigator will also fill a check list, for each visit, to ensure that the picture of the lesion has been taken, and there will also be a checkbox in case of presence of infection in the wound bed.

Regarding the measurement of the size of the lesions, with "length" and "width" it is meant the longest diameter of the lesion and the largest diameter orthogonal to the first.

There is also a section dedicated to recording any additional visits, the date of recovery and the observation period following the end of the treatment. On the last page there is a table for reporting adverse events that will occur during the trial. In this table must be reported all types of adverse events (even serious). In this table will be reported the date of onset of the event, the type of event (there are already some entries of common adverse events that may occur on the wound or in the perilesional tissue), the solution implemented (additional therapy, hospitalization, etc.), the date of resolution of the event, the way of resolution and correlation of the event with topical therapy or treatment with EmoLED. The onset of any adverse event (even not serious or unrelated) must be reported to the sponsor, as well as included in the table above. In case of suspected or established correlation of the adverse event with treatment with EmoLED, the event will be declared as an "incident" and the principal investigator will be obliged to report it to the competent authorities as described in paragraph "Incidents and their reporting".

*Data collection form (Home Care) (Annex C)*

During the home visit phase by the home care staff, a short data collection form will be filled out (twice a week) where in addition to the patient's identification code and belonging to the Treated or Control group, the same parameters of the data collection form will be annotated weekly for the Experimental Center. On the last page there is a table for reporting adverse events (see Annex B).

*Data collection form on Quality of Life (Annexes D, E)*

At the first visit and at the last visit to the experimental center, the enrolled patient will be given a form for the collection of data on quality of life, in which the subject is asked to answer some questions (about autonomy, pain, daily discomfort, etc.) also related to the presence of the chronic lesion under examination.

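### The photosensitisation exclusion is applied at entry, but the protocol requires no check for it during the 20 weeks of blue-light treatment, including on return after an infection

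*Protocol*

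**What the plan says.** The Exclusion Criteria of the protocol bar "Patients with pathologies or under treatment with drugs that induce photosensitization of the skin". The closing paragraph of that section says when the criteria bite: "In order to be eligible for the planned treatment phase, all the inclusion and exclusion criteria must be met". It adds that existing drug therapy is to be kept, and says nothing on drugs started later.

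The section on medical-surgical procedures and follow-up sets two treatments a week for twenty weeks, 40 in all, given at home by the nursing service. It disallows "treatments with other types of phototherapies (including photodynamic therapies), topical negative pressure therapy, or other therapeutic interventions in addition to standard therapy" during that time and until healing. For a wound infection it provides antiseptic dressing and, "if deemed necessary by the investigator, with systemic anti-infective therapy, identified by medical personnel". Participation is interrupted while the lesion shows infection, and then: "The patient can continue the study only if there is a remission of the symptoms of infection".

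Under Study design, "the Investigator at the outpatient center will be blinded to the treatment performed at home by the patient", and for control patients "the operator will simulate to perform the treatment" with the beam pointed away.

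**The concern.** The sponsor judged that a photosensitising drug or disease is reason enough not to give this light. That reason does not end at randomisation: the patient is then exposed up to twice a week for twenty weeks. The protocol itself describes one way in which the situation can arise. A patient becomes infected, receives a systemic agent, improves, and goes back to treatment. If that agent is a photosensitiser and the course is not finished, the patient receives blue light in a state that would have led to refusal at entry. The same holds for a photosensitising drug started for any other reason, or a photosensitising condition that appears during treatment.

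What is at stake is the safety of individual patients in the treated arm. No estimate, test or endpoint is affected.

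**Working it through.** No figure in the protocol is in dispute, so the check sets the relevant sections side by side.

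1. **Where photosensitisation is mentioned.** It appears once, in the Exclusion Criteria, as a condition for entering the treatment phase.

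2. **Whether another rule extends it.**
   - The list of disallowed treatments (medical-surgical procedures) covers other light therapies, negative pressure and interventions added to standard care. It does not name photosensitising drugs, and the next paragraph permits a systemic anti-infective with no limit on the agent.
   - The instruction to maintain existing drug therapy does not restrict new drugs.
   - Registration of clinical data provides space for drug therapy on the data collection form, and for the measures taken on the adverse event page. Neither entry is linked to a decision about the next light session.
   - The early-exit rules (Known or predictable factors) cover missed visits, missed treatments, an unknown recovery date and poor compliance. Photosensitisation is not among them.

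3. **The return rule.** Its wording makes remission of symptoms a necessary condition. It is the only condition stated. Completing the anti-infective course and reviewing the agent are not required.

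4. **Who could catch it.** The investigator who decides on systemic therapy does not know the arm. The nurse who gives the light does know it, but no section assigns the nurse a drug check.

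5. **What a hold would mean under the exit rule.** A patient leaves after more than four consecutive missed treatments, unless the non-treatment is foreseen in the protocol. The schedule is 40 / 20 = 2 sessions a week. Assume fixed days 3 and 4 days apart, which the protocol does not specify. Counting from each possible starting weekday gives:

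| Length of hold | Consecutive sessions missed |
|---|---|
| 14 days | 4 |
| 15 to 17 days | 4 or 5 |
| 18 to 20 days | 5 or 6 |
| 21 days | 6 |

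A hold of up to 14 days therefore stays within the limit. The limit can be passed from 15 days and is always passed from 18. Sessions missed during an infection suspension are exempt and do not count.

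**The case against.** The best answer is that clinicians already have the means to act. Ethical considerations makes the principal investigator responsible for all medical decisions and keeps risk and benefit under review during the trial. Clinical evaluation plan deviations treats a treatment not given as a minor deviation to be recorded, and allows even a major departure without prior approval where it removes an immediate risk. This stands: light may be withheld today. But these are general permissions. They tell nobody to ask about a new drug.

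Second, a reader might infer that remission of symptoms entitles the patient to resume light. The text does not support that. Remission is necessary, not sufficient, and the investigator may prolong the suspension. Because participation stops during infection, this route is limited to a photosensitising agent still in use after symptoms have gone.

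Third, a reader might infer that withholding light would push patients out of the trial. That is not supported either. The exemption in the exit rule gives infection suspension as an example, not as a closed list. The hold would have to fall outside an infection suspension and last at least 15 days on the assumed spacing. Patients who do not complete stay in the intention-to-treat analysis (Management of missing data). Drop-out and exposure are also alternatives: if light is withheld, the exposure does not occur.

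Fourth, blinding does not prevent caution. The investigator knows that every randomised patient may be receiving light and can act on that without unblinding. This is right. The remaining weakness is only that the prescriber and the person giving the light are different people, with no stated check between them.

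Fifth, the User Manual, the operator training and the annexes are not at hand and may contain an on-treatment warning. This cannot be excluded, so the point concerns the protocol text and not the whole trial procedure.

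**Conclusion.** The point holds as a minor, inexpensive safety improvement. As written, the protocol screens for photosensitisation at entry, requires no check for it over the 40 sessions, and allows return after infection without asking which drug is still being taken. It therefore leaves room for light to be given to a patient whom its own criterion would have refused.

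The practical weight depends on a photosensitising drug or condition actually arising during treatment. The protocol names no anti-infective and gives no infection rate or course length, so no patient count can be given. No bias between arms and no likely effect on drop-out is claimed. The conclusion also assumes that the User Manual and annexes do not already contain the check.

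**What to change.** Four small changes to the protocol:

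1. **Exclusion Criteria:** state that the photosensitisation criterion continues to apply through week 20.
2. **Home-care form and procedure:** have the Home Care nurse check for a newly started photosensitising drug or a new photosensitising condition before each session, real or simulated, in both arms. Doing this identically in both arms keeps the patient and the centre investigator masked.
3. **Medical-surgical procedures:** withhold the real or simulated session while the drug or condition is present, and say that this also applies on return after infection, in addition to remission of symptoms.
4. **Known or predictable factors:** name this hold as non-treatment foreseen in the protocol, so that staff need not interpret the exemption.

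Which drugs and conditions count is for the investigators to define, ideally as a short list. The cost is a few sentences, one extra line on the home-care form and a few withheld sessions.
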